#### 5.4 Additional Analyses

#### 5.4.1 Demographics and Baseline Characteristics

Demographic, medical history and other clinically relevant baseline variables, as well as safety data, excluding AEs and SAEs, will be summarized by treatment using descriptive statistics (i.e. number of observations available, mean, standard deviation, minimum, and maximum for continuous variables and counts and percentages for qualitative variables). Dichotomous variables will be evaluated using Fisher's exact tests. Categorical variables will be evaluated by Cochran-Mantel-Haenszel (CMH) Modified Ridit Scores, i.e. CMH of general association for nominal variables and CMH of row mean score for ordinal variables. Continuous variables will be evaluated by a two-sample t-test.

#### 5.4.2 Subgroup Analyses

Additional subgroup analyses are planned for gender. These additional analyses will be conducted as feasible and may be used in combination with all other analyses for drawing conclusions regarding the safety and effectiveness of the investigational device.

#### 5.4.3 Changes to Planned Analyses

Any changes to the planned analyses will be documented as amendments to the Statistical Analysis Plan (SAP) and in the study report.

#### 5.4.4 Interim Analyses

There will be two planned interim analyses and one final analysis for this study (**Table 1**, below). The stopping boundaries are derived using the Triangular Method [see footnote 1], which is a special case of Unified Family (Power) boundaries. A shape parameter ( $\tau$ ) of 0.65 will be used, and both boundaries will be non-binding. Interim analyses will occur when approximately 22 and 60 total subjects have been enrolled with 3-month assessments. The stopping boundaries are

ST 800-A

### STATISTICAL ANALYSIS PLAN

moderately aggressive for both effectiveness and futility to reduce the number of subjects enrolled if clear evidence of effectiveness or futility becomes apparent during the trial. When the design assumptions are correct (40% versus 70%), the chance that the trial will stop for effectiveness at the second interim analysis is about 1 in 3. However, if the Latera rate is 85% as seen in the single arm studies, the chance of stopping for effectiveness at the second interim analysis is better than 8 in 10. While all evaluable subjects enrolled at the time of the interim analysis would be followed through 3 months and included in the primary endpoint, an early termination at the second interim analysis could save 20-30% of the total sample size, depending on the enrollment rate.

Interim analyses will be carried out by an independent statistician and reviewed by the independent DMC. The interim analyses will use an alternative to the critical ratio test given below and described by Fleiss. The test results will be compared to the triangular group sequential boundaries. Additional operational details will be found in the DMC Charter.

$$z' = \frac{|p_2 - p_1| - \frac{1}{2}(1/n_{1.} + 1/n_{2.})}{\sqrt{\frac{p_1 q_1}{n_{1.}} + \frac{p_2 q_2}{n_{2.}}}}.$$

			ndaries value)	Cumulative Error Spending		
Analysis	Evaluable (n)	Futility	Efficacy	Type II	Type I	
Interim 1	22	0.7921	0.0005	0.0106	0.0005	
Interim 2	60	0.2139	0.0090	0.0548	0.0093	
Final	124	0.0194	0.0194	0.1000	0.0250	

Table 1. Group Sequential Trial Design – Boundary Information

<sup>3 Fleiss JL, B Levin, MC Paik. Statistical Methods for Rates and Proportions, 3rd Ed. John Wiley & Sons, 2003, (Ch. 3, p 61).

ST 800-A

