## STATISTICAL ANALYSIS PLAN

The treatment  $(p_T)$  and control  $(p_C)$  will be compared using a 1-sided test for superiority of the following hypothesis:

H0:  $p_T \le p_C$  versus HA:  $p_T > p_C$ 

Where p is the proportion of subjects with a positive response on the primary endpoint assessment. Successful rejection of the null hypothesis will be taken as evidence the device provides reasonable assurance of effectiveness.

A 1-sided binomial test of proportions will be used to compare treatment groups.

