### STATISTICAL ANALYSIS PLAN

SAS Code for Nonbinding Beta Boundary

```
proc seqdesign altref=0.3 errspend BOUNDARYSCALE=pvalue;
onesidederrorspending: design nstages=3 info=cum(3.6 8 20)/*3/20,
10/20=1/2, 1*/
method(alpha)=tri(tau=.65)
method(beta)=tri(tau=.65)
alt=upper stop=both (betaboundary=nonbinding)
alpha=0.025 beta=0.10;
samplesize model = twosamplefreq (nullprop=0.4 test=prop);
ods output Boundary=Bnd_Prop_pt5 ;
run;
```

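### SAP 5.4.4 prints the interim statistic with an absolute difference and no sign rule, so applied literally it loses most futility stops when Latera does not beat sham

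*SAP*

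**What the plan says.** SAP 5.4.4 introduces the interim test with "The interim analyses will use an alternative to the critical ratio test given below". The printed z' has the absolute value of p2 minus p1 in the numerator, less a continuity correction of half of (1/n1 + 1/n2), over an unpooled standard error. The subscripts 1 and 2 are not assigned to Latera or sham. The next step is "The test results will be compared to the triangular group sequential boundaries". No sentence restores a sign or says how z' becomes a p-value.

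The boundaries themselves are directional. In SAP 5.2 the two proportions "will be compared using a 1-sided test for superiority of the following hypothesis", with the alternative that Latera exceeds sham. The code in SAP 5.4.4 has "proc seqdesign altref=0.3 errspend BOUNDARYSCALE=pvalue" and "alt=upper stop=both (betaboundary=nonbinding". SAP 5.4.4 also says "both boundaries will be non-binding". It sends additional operational details to the DMC Charter. Protocol 6.8 refers the interim plan to the SAP and the Charter.

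**The concern.** An absolute difference cannot show that Latera is behind. The look-1 futility limit in the SAP 5.4.4 boundary table, p = 0.7921, corresponds to z = -0.814, so it calls for a statistic that turns negative when sham leads. As printed, z' instead grows as the sham lead grows, and its upper-tail p-value falls. A clear sham lead can then look like an ordinary result to continue.

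At stake is the futility protection. Protocol 8.2 offers interim review, with halting for futility, as a risk mitigation for subjects. If the rule does not work when Latera is no better than sham, more subjects undergo a cannula-only procedure or receive an implant that is not helping.

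**Working it through.** **Inputs.** Looks at 22, 60 and 124 evaluable subjects; futility p 0.7921, 0.2139 and 0.0194; efficacy p 0.0005, 0.0090 and 0.0194 (SAP 5.4.4). Design rates 40% sham and 70% Latera (SAP 2.4). Allocation 1:1 (protocol synopsis), taken as 11, 30 and 62 per arm. Assumption: p = 1 - Phi(z'), since the SAP gives no conversion.

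**The plan's own figure.** Treat the boundaries as limits for a signed one-sided z, with information fractions 22/124, 60/124 and 1. The drift needed for 90% power is 3.513. With unpooled variance 0.7 x 0.3 + 0.4 x 0.6 = 0.45 and difference 0.3, N = 2 x 3.513² x 0.45 / 0.3² = 123.4, so 124. The stated sample size is reproduced on a signed scale.

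**Look 1, as printed.** The largest p arises at 10/11 v 10/11 (or 1/11 v 1/11). The correction is 1/11 = 0.0909 and SE = sqrt(2 x (10/11)(1/11)/11) = 0.1226, so z' = -0.0909/0.1226 = -0.742 and p = 0.771. This is below 0.7921, so no table with a defined z' stops for futility. For splits from 10:12 to 7:15 the largest finite p lies between 0.681 and 0.727.

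**Look 2, as printed.** Latera 12/30 v sham 18/30: numerator 0.2000 - 0.0333 = 0.1667; SE = sqrt(0.24/30 + 0.24/30) = 0.1265; z' = 1.318; p = 0.094. This is below 0.2139, so the trial continues. With the sign, z' = -1.318 and p = 0.906, so it stops.

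There are 465 possible look-2 tables with sham ahead. As printed, 86 stop for futility, 130 continue, 248 with finite z' fall below the efficacy limit, and one (0/30 v 30/30) has zero variance and an undefined z'. No sham lead of 5 or more is among the 86. With the sign, all 465 stop for futility, given the zero-variance rule under the fix.

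**Probabilities by exact enumeration.** The sign is the only change: z' = sign(pT - pC) x max(|pT - pC| - cc, 0)/SE, with cc and SE as printed.

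| True Latera v sham | Futility stop by look 2, printed | Signed | Mean evaluable, printed | Signed |
|---|---|---|---|---|
| 30% v 40% | 53% | 96% | 86.9 | 52.2 |
| 40% v 40% | 69% | 85% | 78.7 | 64.1 |
| 70% v 40% | 9.6% | 9.8% | – | – |

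Mean evaluable subjects assume that futility is followed and do not count subjects enrolled while 3-month data are awaited. Modest imbalance (10:12, 12:10 or 9:13 at look 1, with similar later imbalance) gives 53–57% v 96–97% in the first row and 69–71% v 85–86% in the second.

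**The form of the signed statistic matters at look 1.** A second reasonable version is (pT - pC - cc)/SE. At 11:11 it stops for futility in 66 of 144 tables, against 45 for the form above. Look-1 futility probability is 41% v 14% at 40% in both arms, and 4.6% v 0.55% at 70% v 40%.

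**The case against.** The strongest reply is that the direction is not in doubt. The alternative hypothesis is one-sided, the code specifies an upper alternative, and a futility limit above 0.5 makes sense only for a signed p-value. An independent statistician would probably supply the sign. The futility boundary is non-binding, so the DMC keeps every option. The Charter may hold the rule. The large contrasts also need Latera to be no better than sham, whereas the plan assumes 70% and cites about 85% in single-arm studies.

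Most of this stands and limits the weight of the point. It does not remove it. Non-binding status lets the DMC override a value, but the value put before it should be right. Inferring the direction does not settle the form of the continuity correction, and the two natural forms differ materially at look 1. A futility rule is needed exactly when the device does not work as assumed.

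Three stronger readings are tempting and not supported:

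- A reader might infer that Latera could be declared effective with sham ahead. The 248 look-2 tables below the efficacy limit do follow from the literal text, but acting on them would contradict the stated alternative, and a DMC seeing the response rates is unlikely to do so.
- A reader might infer that the false-positive rate for Latera is inflated. When Latera leads, the printed and signed forms give the same efficacy decision. Latera-favouring type I error is the same either way, 2.3–2.5% over null rates of 20–70% (futility ignored, pooled uncorrected final z assumed).
- A reader might infer that adding the sign makes the rule match the tabulated type II spending. It does not: at 70% v 40% the signed form gives 0.55% against 1.06% at look 1, and 9.8% against 5.48% by look 2.

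**Conclusion.** The point holds as a defect of specification with a real effect on futility. Read literally, the printed statistic cannot trigger the look-1 futility limit at 11:11, and at look 2 it gives no futility stop for any sham lead of 5 or more. It cuts futility stopping by look 2 from 96% to 53% at 30% v 40%, and from 85% to 69% at 40% v 40%. At the design rates the effect is negligible. No false win for Latera follows from it.

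The figures rest on exact or near 1:1 balance, an upper-tail normal p-value, and the tabulated boundaries applied to z' at 22 and 60 evaluable subjects. The DMC Charter could already contain a sign rule. The SAP, which prints the statistic, does not.

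**What to change.** Before the first interim, amend SAP 5.4.4 to state:

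- p2 = pT is the Latera responder proportion and p1 = pC the sham proportion.
- z' = sign(pT - pC) x max(|pT - pC| - cc, 0)/SE, with cc and SE as printed.
- The one-sided p-value is 1 - Phi(z').
- If SE = 0: z' = 0 when pT = pC, p = 0 when pT > pC, and p = 1 when pT < pC.
- This form of the continuity correction is the one chosen, in preference to (pT - pC - cc)/SE.

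The floor at zero stops the sign reversing in unequal arms when the difference is smaller than cc. It changes no stopping decision for splits from 7:15 to 15:7 at look 1 or 22:38 to 38:22 at look 2.

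The cost is one short amendment, with sample size and boundaries unchanged. Power at 70% v 40% falls by about 0.1 point if futility is followed and not at all if it is ignored. The starting level depends on the final test, which SAP 5.2 describes only as "A 1-sided binomial test of proportions will be used to compare treatment groups". With futility followed it is 86.0% for a pooled uncorrected z, 84.1% for z' and 83.9% for a one-sided Fisher test; with futility ignored it is 91.4%, 88.6% and 88.3%. All three tests are assumptions. The remaining mismatch with the tabulated type II spending needs separate attention.

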This Clinical Investigational Plan (CIP), informed consent forms (ICF), recruitment materials, and all participant materials will be submitted to the Institutional Review Board (IRB) for review and approval. Approval of the CIP and the ICF must be obtained before any subject is enrolled. Any amendment to the CIP will require review and approval by the IRB before the changes are implemented to the study. In addition, all changes to the ICF will be IRB-approved and a determination will be made regarding whether a new consent needs to be obtained from subjects who previously provided consent.

INVESTIGATOR SIGNATURE PAGE

Investigator Name

Title

Site Name

Site Number

Date

I have read the protocol and agree that it contains all necessary details for carrying out this study. I will conduct the study as outlined therein.

I agree to keep records on all subject information (e.g., source documents and informed consent forms), device shipments and return forms, and all other information collected during the study, in accordance with local and national regulations.

Investigator Signature

SYNOPSIS

Study Title	Latera RCT – Latera [®] Absorbable Nasal Implant vs. Sham Control for Lateral Nasal Valve Collapse		
Spirox Protocol Number	CP04		
Investigational Device	Spirox Latera Absorbable Nasal Implant		
ClinicalTrials.gov Identifier	NCT 03400787		
Sponsor	Spirox, Inc. [name]		
Study Purpose	To evaluate the Latera Absorbable Nasal Implant (Latera Implant) Implant versus Sham Control in subjects with nasal valve collapse due to or primarily due to insufficient cartilaginous support of the lateral nasal wall		
Objective	The primary objective of the LATERA RCT is to demonstrate the superiority of the Latera Implant to improve nasal breathing, compared with a Sham Control treatment.		
Phase of Study	Post-market		
Study Design	Randomized (1:1), sham-controlled, single-blind, multicenter pos market trial using an adaptive trial design		
Investigational Sites	Up to 15 investigational sites in the United States, in office-based locations with investigators experienced in standard nasal interventions for airway obstructions and the use of the Latera Implant		
Study Population	The Adaptive Design allows for enrollment of up to 150 subjects with nasal airway obstruction due to or primarily due to nasal valve collapse.		

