#### 2.4 Sample Size Considerations

The primary analysis will be based on a 1-sided binomial test of proportions. Assuming a Sham Control response rate of 40% and a Latera Treatment response rate of 70% at month 3, a maximum sample size of 124 evaluable subjects is required for 90% power and preserving a 2.5% (one-sided) type I error rate. This study is designed as a group-sequential trial with 2 interim analyses and a final analysis. The stopping boundaries are derived using the Triangular

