# STATISTICAL ANALYSIS PLAN

Method, which is a special case of Unified Family (Power) boundaries. A shape parameter of 0.65 will be used, and both boundaries will be non-binding.

Interim analyses will occur when approximately 20 and 60 total subjects have been enrolled and have had their 3-month assessment. The Latera response rate has been observed at approximately 85% in single-arm trials and is likely to be slightly lower in a single blind setting. Thus, 70% is likely a conservative estimate. The placebo response rate observed in pain trials is approximately 30%, and may be even higher in a procedural setting, so 40% was selected for the control response rate used in the study design calculations.

Assuming up to a 10% drop out rate and a 10% potential retrieval rate, the sample size is adjusted to enroll up to 150 subjects to assure adequate sample size with 3 months follow up.

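### At interim 1 the unpooled z' does not deliver the tabled Type I error of 0.0005 (about 0.0018 at 11 per arm and a 40% common rate); the trial's overall 2.5% is not thereby exceeded

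*SAP*

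**What the plan says.** SAP 5.4.4 prints the interim statistic in full. Its numerator is the absolute difference in proportions less a continuity correction, and its denominator is the unpooled standard error. The section then says "The test results will be compared to the triangular group sequential boundaries". The row of SAP Table 1 (Boundary Information) for the first look reads "Interim 1 22 0.7921 0.0005 0.0106 0.0005": 22 evaluable subjects, futility p 0.7921, efficacy p 0.0005, cumulative Type II error 0.0106, cumulative Type I error 0.0005.

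On timing, SAP 5.4.4 says "Interim analyses will occur when approximately 22 and 60 total subjects have been enrolled with 3-month assessments", while SAP 2.4 says "Interim analyses will occur when approximately 20 and 60 total subjects have been enrolled and have had their 3-month assessment". Allocation is equal (Protocol Synopsis: "Randomized (1:1), sham-controlled, single-blind").

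The boundaries come from a PROC SEQDESIGN normal-theory design. SAP 2.4 describes them: "A shape parameter of 0.65 will be used, and both boundaries will be non-binding". Neither document reports a small-sample check of z' at 22 subjects. SAP 5.2 names a one-sided binomial test for the primary comparison and does not say which variance it uses.

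**The concern.** A boundary of 0.0005 on the p-value scale spends 0.0005 of the Type I error only if the statistic is close to normal that far into the tail. The unpooled standard error shrinks when one observed proportion is near 0 or 1, or when both are well away from one half. Those are the outcomes that produce large differences. With 11 per arm this effect can outweigh the continuity correction, so z' crosses on results weaker than the boundary implies.

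At stake is what the DMC believes it is seeing. Under SAP 2.1 randomization may end if the efficacy criterion is met at an interim. A crossing at about 22 subjects would be presented as meeting a one-in-two-thousand criterion when the true false-crossing rate may be nearer one in five hundred.

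**Working it through.** **Inputs.** 22 evaluable subjects (SAP 5.4.4), taken as 11 per arm from 1:1 allocation. Efficacy p 0.0005, so z of at least 3.2905. Design rates from SAP 2.4: "Assuming a Sham Control response rate of 40% and a Latera Treatment response rate of 70% at month 3". The null is evaluated at equal rates, with 40% as the plan's own sham value and 20% to 70% as a range.

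**1. The plan's boundary reproduces.** For a one-sided triangular boundary with shape 0.65, Z_k = C(1 + 0.65 t_k)/√t_k, with t = 22/124, 60/124 and 1. Solving for a total of 0.025, with futility non-binding, gives C of about 1.253 and Z = 3.317, 2.367, 2.067. The p-values are 0.00046, 0.00896 and 0.0194 (tabled 0.0005, 0.0090, 0.0194). The table is sound; the question is which statistic is compared with it.

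**2. One outcome by hand: Latera 9/11, sham 2/11.**
- z' numerator: 7/11 − ½(1/11 + 1/11) = 6/11 = 0.5455.
- z' denominator: √(2 × (9/11)(2/11)/11) = √0.02705 = 0.1645.
- z' = 3.317, one-sided p = 0.00046: crosses the tabled 0.0005.
- Pooled z without correction: 0.6364/√(0.25 × 2/11) = 0.6364/0.2132 = 2.985, p = 0.0014: does not cross.
- An exact unconditional p-value is 0.0022.

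**3. The whole region.** Evaluating all 12 × 12 outcomes, z' crosses when Latera responders reach 7, 8, 9, 10 or 11 against 0, 1, 2, 3 or 4 sham responders. At a common rate of 40% the probability is the sum of P(S = s) × P(L ≥ minimum):

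| Sham s | P(S = s) | Latera minimum | P(L ≥ minimum) | Product |
|---|---|---|---|---|
| 0 | 0.00363 | 7 | 0.09935 | 0.00036 |
| 1 | 0.02660 | 8 | 0.02928 | 0.00078 |
| 2 | 0.08868 | 9 | 0.00592 | 0.00053 |
| 3 | 0.17737 | 10 | 0.00073 | 0.00013 |
| 4 | 0.23649 | 11 | 0.00004 | 0.00001 |

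The total is 0.0018, or 3.6 times 0.0005.

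**4. Other rates and splits (false efficacy crossing at interim 1).**

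| Sham/Latera, statistic | 20% | 30% | 40% | 50% | 60% | 70% |
|---|---|---|---|---|---|---|
| 11/11, z' | 0.00023 | 0.00096 | 0.00180 | 0.00217 | 0.00180 | 0.00096 |
| 10/10, z' | 0.00012 | 0.00053 | 0.00105 | 0.00129 | 0.00105 | 0.00053 |
| 10/12, z' | 0.00044 | 0.00130 | 0.00161 | 0.00126 | 0.00072 | 0.00032 |
| 12/10, z' | 0.00008 | 0.00032 | 0.00072 | 0.00126 | 0.00161 | 0.00130 |
| 11/11, pooled z, no correction | 0.00002 | 0.00015 | 0.00034 | 0.00043 | 0.00034 | 0.00015 |

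The last row isolates the cause: with a pooled variance the tabled 0.0005 holds at 11 per arm.

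**5. Sensitivity to rounding.** The 9/11 v 2/11 outcome has z' = 3.3166, while the unrounded boundary is 3.3168. If it is excluded, the 40% figure falls by 0.08868 × P(L = 9) = 0.08868 × 0.00519 = 0.00046, to 0.0013. The 50% figure falls to 0.0015.

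**6. Later looks, with 30 and 62 per arm.** At interim 2 taken alone, z' crosses with probability 0.0055 to 0.0068 at common rates of 30% to 60%, against a boundary of 0.0090. Cumulative error by interim 2 is about 0.006 to 0.008, below the tabled 0.0093. Overall error at these rates is 0.018 to 0.019 with z' at every look, and 0.023 to 0.025 with z' at the interims and a pooled uncorrected final test.

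**7. Chance of an efficacy crossing at 11 per arm.** At 85% v 40%: 22% with z', 10% with pooled z. At 70% v 40%: 7.0% and 2.4%.

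**The case against.** The best defence is that the plan's error claim is for the whole trial ("a maximum sample size of 124 evaluable subjects is required for 90% power and preserving a 2.5% (one-sided) type I error rate") and that this claim is not broken. That stands. The absolute excess at the first look is about 0.0013 to 0.0017 (0.0018 or 0.0022 less 0.0005), and the conservatism of z' at interim 2 more than absorbs it.

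It is also fair that a factor of about four is the least favourable case, needing 11 per arm and a common rate near 50%. Both statements of timing are approximate, an even split is an assumption, and the outcome in step 2 lies almost exactly on the boundary.

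The figures of 22% and 10% do not show that z' stops too often when the device works. Normal theory at 85% v 40% gives about 20%: the drift is 0.45/√((0.24 + 0.1275)/11) = 2.46, and P(Z > 3.29 − 2.46) is about 0.20.

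A reader might infer that effectiveness would be declared automatically on 22 subjects. The documents do not support that. The boundaries are non-binding, an independent DMC reviews the result, and SAP 5.4.4 keeps evaluable subjects already enrolled at the interim in follow-up and in the primary endpoint.

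None of this makes the first row of the table right for the statistic the SAP prescribes.

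**Conclusion.** The concern holds for the first look only. With z' as printed, the tabled Type I error of 0.0005 at interim 1 is not met at the plan's own 40% sham rate. The exact value is 0.0018 at 11 per arm, or 0.0013 if the unrounded boundary excludes 9/11 v 2/11, and 0.0007 to 0.0016 for 10/10, 10/12 or 12/10 splits. At 11 per arm it is about 0.0010 at 30% and 0.0022 at 50%, and there is no excess at 20%.

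A reader might conclude that the trial's 2.5% error is inflated. The calculations do not support that for z' throughout or for a pooled final test. The one reservation is that SAP 5.2 leaves the final variance open: an uncorrected unpooled final test would give at most about 2.6%.

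These results assume the 22, 60 and 124 subjects divide equally between arms, except where another split is stated, and that futility stopping is ignored, as its non-binding status allows. This is a calibration error at one look that a short SAP change corrects.

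**What to change.** In SAP 5.4.4, for interim 1 only, replace z' by one of these, compared with 0.0005:
- an exact unconditional p-value, with the ordering statistic named; or
- the pooled-variance z without continuity correction. Its first-look error is at most 0.00043 at 11 per arm and 0.00047 at 10/12 or 12/10. It can reach about 0.0006 at a 13/9 split, so the exact p-value is safer if the arms are uneven.

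Alternatively, keep z' and restate the first-look Type I figure, with the split and range of rates it assumes.

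At 11 per arm the pooled z crosses only on outcomes where z' also crosses, so changing that look alone cannot raise overall error. Do not extend the uncorrected pooled z to all looks without checking the total. Exact enumeration over 11, 30 and 62 per arm gives about 0.0252 at a 30% common rate and 0.0255 at 33%, just above the limit, against about 0.018 with z' throughout.

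The change is a sentence in the SAP. Its cost is a clearly lower chance of stopping at 22 subjects: about 10% instead of 22% at 85% v 40%, and 2.4% instead of 7.0% at 70% v 40%.
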